All study activities will take place virtually, via a video call, with the exception of the eye tracking tasks, which will take place in the EIRG lab. After consent (explained below), all participants will complete the following pre-test child assessments, outlined in the table below. Given the nature of home testing the numbers of visits may vary based on timepoint and family. **Baseline only for children without hearing loss**: Children within the same age range who are typically developing without hearing loss will be invited to participate in pre (T0) testing only. Testing will remain in person (if allowed) for baseline only children.

Following pre-test, the naïve assessor and parent will complete monthly assessment visits with each child and parent in their home via video call for the entirety of the study (T1 - T24). During these visits, the assessor will collect a 12-minute language sample and a 12-minute parent child interaction. Parents will also complete parent surveys, which will be sent via email and include a REDCap link.

In addition to the monthly assessment sessions, the naïve assessor will also complete additional assessments with parent assistance at T0 (baseline, T7 (post-test) and T24 assessment (follow-up) via video call.

The parent and child will also participate in recorded video sessions with their speech therapist (SLP) two times throughout the study. For parents in Illinois, they parent and child will also be asked to participate in a video session with the child's developmental hearing therapist (DTH). This will not be done with parents in other states, since DTH services can vary by state. The parent videotape a typical early intervention session that takes place in the home. The video recorded sessions will be

Page 5 of 20 Revised: May 25, 2018

stored with all other research data, on password protected servers and drive. This component of the study allows researchers to see what other services parents and children are receiving in the community. After each early intervention therapy visit, the parent will also complete several surveys about the visit and the therapist.

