The child's SLP and/or DTH will be consented separately. They will each complete separate video-taped sessions up to 2 times over the course of the child's participation in the study – around month 4 and when the child is 30 months old. After each session, the therapist will be asked to complete surveys. If the child is not receiving speech or developmental services in the home, or if the therapist does not consent to this research, the child and parent can still participate in this research study.

Table 1. Summary of assessments

Assessment	Description	Participant	Duration	Location	Time Point
Communication and Symbolic Behavior Scales (CSBS)	The child is presented with toys and activities designed to elicit prelinguistic communication. The interaction is video recorded and then scored.	Parent and Child	30 min.	Home or Lab	Pre (T0) Post (T7)
Preschool Language Scale - Fifth Edition (PLS-5)	The child is presented with different receptive and expressive tasks such as following simple directions and labeling pictures until the child provides an incorrect response to six consecutive items for both auditory comprehension and expressive communication subscales	Child	30 min.	Home or Lab	Pre (T0) Post (T7) Follow- up (T24)
Language Sample	The child plays with four different sets of toys and looks at a wordless picture book, while the parent engages with the child but does not talk.	Child	12 min.	Home or Lab	Pre (T0) Monthly
Parent-Child Interaction	The child and parent play "as they usually would" with a set of toys for 12 minutes.	Parent and Child	12 min.	Home or Lab	Pre (T0) Monthly
TELE-ASD-PEDS	Virtual screening assessment for autism, Parents will be offered this assessment if the parent or the clinical team has concerns the child may have autism during the regular course of the study. Parents will also have the opportunity to consent to this assessment at 36-months.	Parent and Child	35-60 min.	Home	At parent request or with parent consent at 36- months

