Early Intervention Therapist Observation Surveys for parent	Parents will complete the following surveys after each individual observation with either their SLP or DTH: (1) About my SLP, (2) Satisfaction Survey, (3) Working Alliance Short Form, (4) Measure of Process of Care, (5) Communication Method Advice	Parent or Secondary Parent	30 min.	Home - but not during the home visit	Beginning of study (~T4) End of study (~30 months old)
Early Intervention Therapist Observation Surveys for therapist	After the videotaped session, the E.I. therapist will be emailed several surveys asking about their clinical background and experience, knowledge of evidence-based practice, and rapport with the parent. Surveys could include: Working Alliance Short Form, Believe About Participation-Based Practices, SLP/DTH Demographics, SLP/DTH Background, SLP/DTH Approach, Hearing Loss Education and Experience, Hearing Loss Approach, Communication Method Advice	SLP or DTH	60 min	Home - but not during the home visit	Beginning of study (~T4) End of study (~30 months old)

Participants assigned to the PICT condition will receive weekly 60-90 minute long intervention sessions in their home via video call for 6 months. Parents will learn four sets of communication support strategies: (a) visual (e.g., modeling language within the child's line of sight), (b) interactive (e.g., following the child's attentional focus), (c) responsive (e.g., responding to all communicative attempts), and (d) linguistically stimulating (e.g., modeling language targets, expanding child communication). Intervention sessions will include the following components:

1. CCX: a 6-minute parent child interaction

Page 10 of 20 Revised: May 25, 2018

- 2. Teach: 10 minutes of the therapist describing the target intervention strategy
- 3. Video Feedback: 8-15 minutes of video feedback for the parent to watch themselves practicing the strategies (review phase only)
- 4. Model: 6-10 minutes of watching standard video clips of parents using the strategy
- 5. Coach: 20 minutes of the parent practicing the strategy with their child with coaching from the therapist
- 6. Review: 5-10 minutes of the therapist reviewing the session with the parent, summarizing the session, and answering the parent's questions

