Data obtained from participants will include standardized, observational, and parent-report measures. All standardized and observational measures will be conducted by independent observers and assessors naïve to the experimental condition. Pre-test assessments will be administered in the participant's home via video call, with the exception of eye tracking measures for local participants. All additional time points will be conducted in the family's home. All standardized assessments and observational measures will be video recorded and coded. Parent report surveys will be collected using REDCap online surveys. Parents will be sent a unique link that gives them access to their unique list of surveys to be completed for that study time point. All surveys and assessments should be completed within a 10-day window to ensure data accuracy at each timepoint. Personal identifiable information (PII) (name, address, phone number, email address) will be collected on all parent/child dyads for the purposes of scheduling assessment visits, for conducting home intervention sessions, and for collecting survey data. Images of the face will be collected by video for the purpose of transcribing and coding parent-child interactions. Date of birth will be collected to determine child age at each time point so that we may include age in months in statistical analyses.

We propose a set of statistical analyses that firmly integrate our hypotheses and research design into a structural equation modeling framework to create a cohesive analytic plan that spans all study aims. Our aims further bridge the divide between

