The data will be monitored by the staff statistician and [name]. They will conduct the randomization, oversee data entry procedures, manage the database, train study staff on data entry procedures, and be responsible for maintaining the quality and integrity of the database as outlined below. Data entry will be completed using a centralized internet-based system (REDCap), which makes the project database instantly available to all authorized researchers in the system and permits access from any computer with an internet connection from multiple locations (via password protected logon). Summary reports (e.g., recruitment, assessment progress) can be generated immediately and are automatically updated with additional data. Reports can be created that document participant progress to-date and track missing data. These missing data reports will be reviewed weekly by the study team, such that we may try to acquire missing data in a timely manner (re-emailing or calling study participants to complete surveys; re-administering test items in the event that not all items were completed).

All data will be independently entered by two different research staff. Discrepancies between records will be automatically identified and verified. Additional quality assurance checks will be completed to check for missing data, range, and outliers. Once the data have been verified, they will be stored in a second "clean" dataset. Summary reports of the "clean" dataset will be organized by time point and measure. The "clean" dataset and summary reports will be reviewed quarterly by the independent biostatistician on the Data and Safety Monitoring Board. Outcomes by experimental condition assignment (intervention, control) will not be included in any interim reports.

Risks related to incorrect or biased scoring of measures will be minimized in the following ways. All standardized and observational measures will be conducted by independent observers and assessors naïve to the experimental condition. All testing sessions will be video recorded and procedural fidelity for test administration will be measured monthly to assess and ensure accuracy of test administration. Observers for all observational measures will be trained to point-by-point reliability of 90% for three consecutive administrations prior to coding the observational data. A second independent observer will code 20% of the observational measures. When reliability

Page 18 of 20 Revised: May 25, 2018

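### The naïve assessor role collects the monthly parent-child interaction and also gives the T7 and T24 tests, so the arm may be guessable, and no stated safeguard limits this exposure

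*Protocol*

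**What the plan says.** Protocol section 8.0 gives one role two jobs. First, "the naïve assessor and parent will complete monthly assessment visits with each child and parent in their home via video call", from T1 to T24, and at each visit "During these visits, the assessor will collect a 12-minute language sample and a 12-minute parent child interaction". Second, "the naïve assessor will also complete additional assessments with parent assistance at T0 (baseline, T7 (post-test) and T24 assessment (follow-up) via video call". Protocol Table 1 places the CSBS at T0 and T7 and the PLS-5 at T0, T7 and T24.

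The interaction is free play "with a set of toys for 12 minutes". SAP Table 1 lists what is coded from it: line-of-sight communication, mirroring and mapping, contingent responses, imitating and adding a word, and similar behaviours. In PICT sessions, "Parents will learn four sets of communication support strategies", and the coded behaviours correspond to these. SAP Aim 1 (analysis 1.1) predicts more strategy use in the intervention arm.

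On masking, section 8.0 states: "All standardized and observational measures will be conducted by independent observers and assessors naïve to the experimental condition". Section 17.0, under Data Monitoring, repeats this first in a list introduced by "Risks related to incorrect or biased scoring of measures will be minimized in the following ways". The rest of the list is video recording of testing, monthly procedural-fidelity checks, coder training to 90% agreement, second coding of 20% of observational measures, and second-person verification of norm-referenced scoring.

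**The concern.** The visit procedure repeatedly shows the person who must stay naïve the behaviour that the treatment is meant to change, and the same role then gives the tests. The documents set no order for the interaction and the tests within a visit, name no separate assessor for T7 or T24, and plan no check of masking. They also do not say whether one observer may code both a family's interaction and that child's CSBS or language sample.

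At stake are the two observed test endpoints: CSBS at post (analysis 1.2b) and PLS-5 at follow-up (analysis 3.2b). The PLS-5 continues until six consecutive incorrect responses, which the examiner judges live. The CSBS is elicited live and scored later from video, by a scorer not said to be someone other than the assessor. An examiner who suspects the arm could prompt, wait or credit differently without intending to. The coded language sample (analyses 1.2a and 3.2a) carries a similar risk at the coding stage.

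**Working it through.** **The plan's own figures.** Assumptions, since the documents state neither: two-sided alpha .05 and 1:1 allocation. A noncentral t with N-3 degrees of freedom (one pre-test covariate) gives, at n=86, 99.8% power for d=1.07, 79.8% for d=.61 and 90.2% for d=.71. At n=96 it gives 80.3% for d=.58 and 90.1% for d=.67. The stated figures reproduce. The concern does not touch them, because the change proposed here leaves N as it is.

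**Exposure.** The monthly visits T1-T6 precede T7, so up to six interactions. T1-T23 precede T24, so up to 23. These are maxima, because the text names a role and not an individual.

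**How well could the arm be guessed?** Assume that visible strategy use differs between arms by d, with equal spread.
- One interaction: P(correct) = Φ(d/2). For d=1.07, Φ(.535) = 70%. For d=.61, Φ(.305) = 62%.
- Average of six with within-parent correlation r: d_eff = d / √((1+5r)/6). The divisor is .866, .764 and .645 for r = .7, .5 and .3.
- d=1.07: d_eff = 1.24, 1.40, 1.66, so 73%, 76%, 80% correct.
- d=.61: d_eff = .70, .80, .95, so 64%, 66%, 68% correct.

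An assessor with no information would be right 50% of the time.

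**What would that do to an endpoint?** Suppose that scores shift by b SD toward the guessed arm (assumption; the documents give no figure). The spurious effect is b(2p-1), where p is the proportion of correct guesses. At p=.76, 2p-1 = .52. The rejection rate under no true effect comes from the noncentral t with 83 df and noncentrality = spurious effect × √(86/4).

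| b | spurious effect (SD) | false-positive rate |
|---|---|---|
| .1 | .052 | about 6% |
| .2 | .104 | about 8% |
| .3 | .156 | about 11% |

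At p=.70 (one interaction, d=1.07) the three rates are about 5%, 7% and 9%.

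**Gradual build-up.** Analysis 1.1 models a slope, so a constant d=1.07 from T1 is generous. If the difference rises linearly to 1.07 at T7, the mean over T1-T6 is 1.07 × 3.5/7 = .535. Dividing by .764 (r=.5) gives d_eff = .70 and 64% correct (62-66% for r = .7 to .3). With b=.3 the spurious effect is .3 × .274 = .08 SD and the error rate 6.6%. A guess that weights the six visits optimally would be right 71-75% of the time, with an error rate of 9-10%.

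**The case against.** A reader might infer that the interaction reveals the arm and that masking has failed. The documents do not support that. The figures above describe an arm that can be guessed with error. Both arms keep their early intervention services, so control parents may show similar behaviour. No text says that one individual follows a family through the study, although none excludes it. Φ(d/2) is also a best case: it assumes a guesser who works from coded scores and knows both group distributions.

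The inputs are soft too. The pilot d=1.07 is given for Aim 1 main effects without naming the outcome, so applying it to visible parent strategies is an assumption. The score shift has no source in the documents.

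The listed safeguards deserve weight. Scoring the CSBS from video and verifying norm-referenced scores both reduce scoring bias, and fidelity checks bear on administration. What remains is that none of them stops the examiner from seeing the parent's behaviour, and re-scoring cannot undo differences in how a response was elicited.

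The coder point is an argument from silence. The protocol requires independent, naïve observers, and nothing shows that one observer in fact codes both samples for a family. The gap is only that no assignment rule is stated.

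Finally, test order at T7 and T24 cannot undo exposure at earlier visits, and parent behaviour stays visible during the CSBS and wherever the parent assists. These objections limit the size of the concern and what reordering can achieve. They do not close the gap.

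**Conclusion.** The concern holds as a threat to masking that the plan does not address. It is not a demonstrated loss of masking. Section 8.0 gives one role both the exposure and the endpoint tests, while sections 8.0 and 17.0 rely on that role being naïve. Under the stated assumptions (visible d between .61 and 1.07, r between .3 and .7, a shift of .1 to .3 SD, two-sided .05, 1:1), correct guessing is about 62-70% after one interaction and 64-80% after six. At 76% correct the 5% error rate becomes about 6-11%, and it is lower if the arms diverge gradually. These figures show only that a modest bias is plausible. The change is worth making because it is cheap.

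**What to change.** In Protocol section 8.0 and the observer paragraph of section 17.0, state that:

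1. No observer codes both a family's parent-child interaction and the same child's CSBS or language sample. This can also be applied to recordings already made but not yet coded.
2. At T0, T7 and T24 the CSBS and PLS-5, where scheduled, are completed before the parent-child interaction, and the interaction is the last task at every monthly visit. T0 precedes randomization; it is included so that pre-test and later scores are obtained in the same order.
3. Among the existing naïve assessors, where scheduling allows, the T7 and T24 tests go to one who has not collected that family's interactions. This is the item that deals with exposure at earlier visits.

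Having the assessor start the recording and then neither watch nor listen would remove more exposure. It should not be adopted unless it is reconciled with section 17.0, which requires staff to log after every session events such as prolonged crying by parent or child.

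The cost is some scheduling and coder-assignment work with the same staff, visits and sample size. Toddlers may be more tired during the interaction at the long visits, which affects the analysis 1.1 measure but applies equally to both arms. Parent behaviour during the CSBS and while assisting with tests remains a residual cue.

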The sample consists of 96 children with bilateral hearing loss and one of their caregivers (mother, father, grandparent). Children of all races and genders will be included in the sample. All children will be between 12 and 18 months of age) at the start of the study. Children will have a diagnosis of bilateral hearing loss. This age was chosen for several reasons. First, this is the age at which intentional communication usually emerges and prelinguistic communication skills develop. As such, this age is necessary to study the effects of early intervention on prelinguistic skills for young children with hearing loss. Second, children are typically seen for an audiology visit during this time, so it is an easy time to enroll study participants. Third, the majority of children are wearing hearing aids at this time. Fourth, 12 months is an age when we are able to test developmental processes that may influence response to intervention. Fifth, parents may be more likely to participate in research when their baby is older and after they have had time to process the diagnosis. Children will start the study around 12-18 months of age and continue in the study for 24 months.

Given a sample size of 86 (96 recruited participants with 10% attrition), we project greater than 99% power for main effects of the intervention (Aim 1) as large as those shown in our pilot study (d=1.07) (see Justification and Feasibility in Research Strategy). We further project 80% power for effects as low as d=.61 and 90% for d=.71. Each of the three previous estimates assume control for pre-test and 10% attrition (e.g., n=86). Our research group has maintained greater than 95% retention in comparable studies over the last two years. We would retain power for smaller effect sizes of d=.58 (80% power, down from d=.61) and d=.67 (90% power, down from d=.71) if no attrition occurs.

5.0 Research Locations:

All study procedures will occur in the homes of participants or at the Early Intervention Research Group at Northwestern University under the supervision of the principal investigator ([name]). Video conferencing services (such a zoom) will be used for all sessions, with the exception of "baseline only" activities and "eye tracking" activities.

Page 3 of 20 Revised: May 25, 2018

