Social Engagement Eye-Tracking Task	The child participates in two consecutive engagement conditions with animal hand puppets as the stimuli: (a) joint attention, (b) unavailable. Each condition includes six trials (six different puppets coming out of an opening). In the joint attention condition, the caregivers will respond only after the child vocalizes or gestures by looking back and forth between the puppet and the child and talking about the puppet. In the unavailable condition, the caregiver will read a book silently and will ignore all child communicative behavior.	Child (Chicagolan d participants only)	5 min.	Lab (if allowed by the state)	Pre (T0)
Communicative Insightfulness Assessment	The parent watches video clips of their child and determines when and why their child is communicating.	Parent (Chicagolan d participants	30 min.	Lab (if allowed by the state)	Pre (T0)

Revised: May 25, 2018

		only)			
Word Learning Eye-Tracking Task	Children will be presented with 29 trials total. On the first two trials, children will be familiarized to the task by seeing two familiar objects on the screen and asked to find one of them. Children will then be presented with images of two novel objects in order to familiarize them with the objects. Following this, children will see 2 movies, each 24 seconds long, that teach the child the name for reach of those new objects ("blick" and "modi"). After this, children are presented with four blocks of test trials. In each test block, children are given 4 test trials in which they are asked to find one of the new objects, and two reminder trials, where the new objects are shown and named in isolation.	Child (Chicagolan d participants only)	6 min	Lab (if allowed by the state)	Follow-up (T24)
Audiology Record Requests	Audiology records will be obtained to confirm degree of hearing loss. The parent will be asked to sign a specific hospital release form, so that we can request the child's audiology records.	Parent	NA	NA	Pre (T0) Post (T7) Follow-up (T24)
	SLP/DTH M		T < 0	1	T =
Early Intervention Therapist Observation (SLP, DTH)	The parent and child will participate in their typical therapy session with their SLP or DTH in their home and the session will be video recorded.	Parent/Careg iver and Child and SLP or DTH	60 min.	Home	Beginning of study (~T4) End of study (~30 months old)

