9.0 Incomplete Disclosure or Deception: NA

10.0 Recruitment Methods:

Children will be recruited through Lurie Children's Hospital, pediatricians, Early Intervention providers, conferences, and online advertising. Participants are recruited in the Chicagoland area and nationally in the U.S. Clinicians who work with families of young children with hearing loss will be given a flyer to give to potentially eligible families. Clinicians may also direct them to our eligibility screener via the text-to-contact number on the flyer, where the caregiver will answer basic self-reported eligibility questions and give permission for EIRG study staff to contact them about their potential study participation. Study staff will then contact families that may be eligible for the study. Interested families may also contact EIRG directly via email, phone, or completing a recruitment survey on the EIRG website. **Baseline only for children without hearing**

Page 12 of 20 Revised: May 25, 2018

loss: Parents of children without hearing loss and with typical development will be invited to participate in baseline testing only.

11.0 Consent Process:

All consent forms will be approved by Northwestern University's Institutional Review Boards (IRB). All informed consent documents will contain the following: (a) an explanation of the purpose of the research, (b) expected duration of participation, (c) a description of research procedures, (d) foreseeable risks, discomforts, and benefits, (e) confidentiality and privacy of records and data, (f) contact information for who to contact to answer questions about the research process or participant rights and, and (g) a statement that participation is voluntary and that refusal will not result in penalty or change in their clinical services. Additional consent elements will also include financial information, alternative treatments, funding source, mandated reporter language, clinical trial information, and optional elements. All consent documents will contain layman's terminology when possible and use language appropriate to an 8th grade reading level. Consent documentation will include the date of IRB approval.

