This aim builds on the analyses of the first to identify moderators of intervention effects by way of SEM-based regression. Identifying moderators of intervention effects will allow us to better understand the effects of intervention and better identify factors that influence response to intervention. In Aim 2, we predict that: (a) parents who show greater insight regarding the intent of their child's prelinguistic communicative behaviors (have greater communicative insightfulness) at pre-test will have a larger intervention effect (2.1) and (b) children who associate their prelinguistic communicative behaviors with responses from their parents (have greater sensitivity to social contingency) at pretest (analyses 2.2a and 2.2b) and (c) have a greater attention to spoken language at pre-test will have a larger intervention effect (analyses 2.3a and 2.3b). Analysis 2.1 uses the proportion of child communicative acts that parents correctly identify (communicative insightfulness) as a moderator of a latent variable that describes overall parent use of strategies measured monthly from 12 (pre) to 18 months of age (post). Analyses 2.2a and 2.2b uses child sensitivity to social contingency (interaction ratio from a still-face procedure at pre-test) to moderate growth in child prelinguistic communicative acts from a

language sample measured monthly from 12 months (pre) to 18 months of age (post) (analysis 2.2a) as well as CSBS Total Scaled Scores at 18 months (post) (analysis 2.2b). In analyses 2.3a and 2.3b, child attention to spoken language (orienting time toward speech from a sequential looking preference procedure at pre-test) moderates the same two outcomes as in 2.2a and 2.2b (growth in child prelinguistic communicative acts, CSBS Total Scaled Scores).

Moderation. Moderation in clinical trials deals with differential effectiveness of intervention as a function of other independent variables. This is typically accomplished with interaction terms, which mathematically state that the effect of an intervention goes up with increases in specific covariates. We will employ all current standards for regressions using interaction terms, including variable centering, ⁹⁰ application of variance inflation factors to test for multicollinearity, ⁹¹ and residual diagnostics to ensure valid and interpretable estimates.

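### Protocol Table 1 limits the Communicative Insightfulness Assessment to Chicagoland parents in the lab, while the text puts everything except eye tracking on video call; if the table governs, Analysis 2.1 has no moderator for non-local families and falls short of its stated power

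*Protocol*

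**What the plan says.** Protocol section 8.0, Table 1, lists the Communicative Insightfulness Assessment as a 30-minute task at T0. The participant is the parent, Chicagoland participants only, and the location is "Lab (if allowed by the state"). The description is one sentence: "The parent watches video clips of their child and determines when and why their child is communicating". Unlike most of the Chicagoland-only rows around it, this row does not carry the eye-tracking label, and its participant is the parent rather than the child.

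The running text differs. Section 8.0 says: "All study activities will take place virtually, via a video call, with the exception of the eye tracking tasks". The same section later repeats that pre-test assessments are done at home by video call, with eye tracking for local families as the exception. Section 5.0 makes the same rule and adds one exception, for baseline-only activities. Section 8.0 uses that term for typically developing children without hearing loss, who are tested at T0 only.

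On recruitment, section 10.0 says: "Participants are recruited in the Chicagoland area and nationally in the U.S".

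The SAP, under Aim 2 Analyses, says: "Analysis 2.1 uses the proportion of child communicative acts that parents correctly identify (communicative insightfulness) as a moderator". The entry for Analysis 2.1 names the Communicative Insightfulness Assessment at pre-test as the source and gives no other. Neither the Aim 2 section nor the Power Analysis mentions a Chicagoland subset or a reduced sample for this analysis.

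**The concern.** Staff who follow Table 1 will give the assessment only to local families who come to the lab. Staff who follow the text will give it to everyone by video call. These lead to different datasets for Analysis 2.1.

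Under the table, every family recruited from outside the area lacks the moderator. The loss is permanent, because a score taken once treatment has begun is no longer a pre-test moderator. The SAP's reliance on full information maximum likelihood does not repair it. In the multiple-group form that the SAP describes, the interaction is the difference between arms in the slope of parent strategy use on insightfulness. A family with no insightfulness score informs the mean and variance of the outcome in its arm, but adds little or nothing to that slope. The SAP does not say how a missing moderator would enter the interaction.

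Two things are then at stake: the power claimed for Aim 2, as it applies to 2.1, and whether a finding about insightfulness applies to the national sample or only to local families.

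**Working it through.** **Step 1: can the table and text be read together?**

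| Source | Who | Where |
|---|---|---|
| Table 1, this row | Chicagoland parents only | Lab |
| Section 8.0, general rule | All enrolled families | Video call, except eye tracking |
| Section 8.0, pre-test rule | All enrolled families | Home video call, except eye tracking for local families |
| Section 5.0 | All | Video, except eye tracking and baseline-only activities |

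The baseline-only exception concerns children who are not randomised, so it does not cover this row. The eye-tracking exception covers it only if that phrase stands for anything done at the lab visit, which the documents do not say.

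**Step 2: reproduce the SAP's moderator power.** Inputs from the SAP Power Analysis: 80% power at R² = 0.078 and 90% at R² = 0.104; 96 recruited, 86 after 10% attrition. Alpha, sidedness and the N used for Aim 2 are not stated. I assume two-sided alpha 0.05 and one added term tested by noncentral F, with k = 3 predictors (1 to 6 makes almost no difference):

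f² = R²/(1 − R²), λ = f² × N, df = (1, N − k − 1).

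- R² = 0.078: f² = 0.078/0.922 = 0.0846
- R² = 0.104: f² = 0.104/0.896 = 0.1161

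| N | λ at 7.8% | Power | λ at 10.4% | Power |
|---|---|---|---|---|
| 96 | 8.12 | 0.805 | 11.14 | 0.910 |
| 86 | 7.28 | 0.760 | 9.98 | 0.877 |

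The stated 80% and 90% match N = 96 to within about one point, and do not match N = 86. Using f² = R² without conversion gives 0.773 and 0.878 at N = 96. A one-sided 0.05 test gives 0.882 and 0.952 at N = 96. Neither fits at N = 96, nor do they fit at N = 86 (0.726 and 0.840; 0.849 and 0.932).

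**Step 3: apply the Table 1 restriction.** The local share is not in the documents, so a range is shown. It is applied to 96 families, with every local parent assumed to be assessed.

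| Local share (assumed) | n | Power at 7.8% | Power at 10.4% | Variance share detectable with 80% power |
|---|---|---|---|---|
| 100% | 96 | 0.805 | 0.910 | 7.7% |
| 75% | 72 | 0.682 | 0.813 | 10.1% |
| 50% | 48 | 0.504 | 0.636 | 14.6% |
| 25% | 24 | 0.274 | 0.356 | 26.6% |

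Put as precision: with equal residual variance and moderator spread, the standard error of the interaction grows by 1/√(share), that is 1/√0.75 = 1.15, 1/√0.50 = 1.41 and 1/√0.25 = 2.00.

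With 10% attrition as well, 75%, 50% and 25% of 86 give n = 64, 43 and 22, and power at 7.8% of 0.629, 0.460 and 0.253.

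**The case against.** The strongest reply is that the restriction may be deliberate. Table 1 names the participant group specifically, the row sits among lab tasks, and one sentence does not say where the clips come from, how they are prepared or what scoring needs. Remote delivery is plausible, since the PICT sessions already use video feedback and model clips over video call, but it remains an inference. This stands, and it is why the remedy has two branches. It does not remove the conflict: if the restriction is intended, the general statements in sections 5.0 and 8.0 need an exception, and the SAP needs the reduced n.

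Four stronger readings are tempting, and the documents do not support them:

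- A reader might infer that national families certainly have no moderator value. That follows only if Table 1 governs; under the text, every family can be assessed.
- A reader might infer that 2.1 rests on self-selected local volunteers, because section 11.0 makes the eye-tracking activities optional. That option names eye tracking, and this task is not described as eye tracking. Extra loss among local families is not stated.
- A reader might infer bias in the comparison of arms. Dyads are randomised individually, so the arms remain comparable within the local subset.
- A reader might extend the contradiction to Analyses 2.2 and 2.3. Their candidate tasks in Table 1 are also Chicagoland-only, but they are labelled as eye tracking, so there the table and text agree. Correcting this row leaves those analyses restricted.

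The point concerns one moderator analysis. The main-effect analyses in Aims 1 and 3 are not affected.

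**Conclusion.** The inconsistency between Table 1 and sections 5.0 and 8.0 is established from the text and needs no calculation. Its consequence is conditional. If Table 1 governs, the moderator power in the SAP is not delivered for Analysis 2.1: at 7.8% of variance it is about 0.68, 0.50 or 0.27 rather than 0.80, for local shares of 75%, 50% or 25%. If the text governs, up to 96 families can contribute and the stated power stands.

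The figures rest on a two-sided alpha of 0.05, a single-term regression approximation to a latent-variable model, and local shares that the documents do not give. They show how sensitive the analysis is; they do not estimate the loss in this trial. That the SAP used N = 96 for Aim 2 is inferred from the match. The harm is to precision and to the population the answer covers. The point should be corrected, but it does not threaten the trial's main conclusions.

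**What to change.** Reconcile Table 1 with sections 5.0 and 8.0.

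- **If the clips can be prepared and shown remotely:** change the row to all participating parents, home video call, Pre (T0). Section 8.0 already places randomisation after the baseline assessments, so no new timing rule is needed. Record the mode of administration and include it as a covariate in Analysis 2.1.
- **If the lab restriction is deliberate, or for families already enrolled without the assessment:** do not collect it after treatment starts. State in the SAP the n available for 2.1 and that the result applies to local families, restate the Aim 2 moderator power for that n, and write the exception into sections 5.0 and 8.0.

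The documents do not give enrolment status. If enrolment is complete, only the second branch remains, and it costs a few sentences.

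The first branch costs one table row, a 30-minute T0 item for each non-local family, and clip preparation and scoring within the protocol's 10-day assessment window. Its drawback is that, where some parents were assessed in the lab and others by video, mode is partly confounded with location, and a covariate cannot fully separate the two.
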